## **4. TREATMENTS**

### **4.1 INVESTIGATIONAL TREATMENTS**

The investigational product BI 765080 has been manufactured by BI Pharma GmbH & Co. KG.

#### **4.1.1 Identity of the Investigational Medicinal Products**

The characteristics of the reference (R) product are given below:

Substance: BI 765080

Pharmaceutical formulation: Powder for solution for injection/infusion

Source: BI Pharma GmbH & Co. KG, Germany

Unit strength: 50 mg/vial

Posology: 2-0-0

Route of administration: IV infusion

Duration of use: Single dose

The characteristics of the test (T) product are given below:

Substance: BI 765080

Pharmaceutical formulation: Powder for solution for injection/infusion

Source: BI Pharma GmbH & Co. KG, Germany

Unit strength: 50 mg/vial

Posology: 2-0-0

Route of administration: SC administration

Duration of use: Single dose

At the time of use, the IV and SC solution for dosing will be prepared as detailed in the instruction given in Appendix [10.1](#).

#### **4.1.2 Selection of dose in the trial**

The dose of 100 mg of BI 765080 selected for this trial has been selected to correspond to the

potential dose for maintenance treatment in clinical trials in patients.

#### 4.1.3 Method of assigning subjects to treatment groups

Prior to the start of the study, subjects willing to participate in this study will be recruited to treatment groups according to their temporal availability (this includes the ability to participate as well in the IV-arm as in the SC-arm). From the eligible subjects matched pairs (based on age and body weight, see Section 3.3) are formed by the investigator.

The randomisation list will be provided to the trial site in advance. Subjects are then assigned to treatment according to the randomization list with a block size of 2. The allocation of these two random numbers to one matched pair of subjects will be done by drawing lots in the morning of Day 1.

Once a random number has been assigned to a subject, it cannot be reassigned to any other subject.

#### 4.1.4 Drug assignment and administration of doses for each subject

The treatments to be evaluated are outlined in Table 4.1.4: 1 below. Each subject will receive one single dose of trial medication. Detailed instructions for the dilution of the trial product, the preparation of the IV infusion and SC injection solutions, the volume to be administered and the infusion/injection time is provided in Appendix 10.1. In the subjects with IV, the infusion solution will be intravenously administered over 30 minutes.

Table 4.1.4: 1 Dosage and treatment schedule

Dose Group	Route of administration	Application volume	Total dose
1	IV	50 mL	100 mg
2	SC	2 mL	100 mg

## Subcutaneous injection

Following an overnight fast of at least 10 hours, the medication will be administered. Trial drug will be injected subcutaneously within 60 seconds in the abdominal region. Detailed handling instruction see Appendix [10.1](#). Subjects will be kept under close medical surveillance until 72 hours following drug administration. On Day 4, subjects will be discharged from the trial site and further assessments will be conducted in an ambulatory fashion For restrictions with regards to diet, see Section [4.2.2.2](#).

## Intravenous infusion

Following an overnight fast of at least 10 hours, the medication will be administered. The infusion solution will be administered intravenously over 30 minutes. Start and time of the

Proprietary confidential information © 2021 Boehringer Ingelheim International GmbH or one or more of its affiliated companies

infusion will be recorded. Detailed handling instruction for the infusion see Appendix [10.1](#). Subjects will be kept under close medical surveillance until 48 h following drug administration. Day 3, subjects will be discharged from the trial site and further assessments will be conducted in an ambulatory fashion. For restrictions regarding diet, see also Section [4.2.2.2](#).

The administration of the trial medication will be done under supervision of the investigating physician or a designee. For drug administration, the so-called four-eye principle (two-person rule) should be applied. For this, one authorised employee of the trial site should witness the administration of trial medication, and – if applicable – its preparation (e.g. reconstitution), if correct dosage cannot be ensured otherwise. For the purpose of drug accountability, the infusion set will be weighed before and after drug administration.

#### **4.1.5 Blinding and procedures for unblinding**

No blinding will be performed. This Phase I trial will be handled in an open fashion throughout (that is, during the conduct, including data cleaning and preparation of the analysis). This is considered acceptable because the potential for bias is low and does not outweigh practical considerations.

Emergency envelopes will not be provided, because the trial medication is known to investigators and subjects.

PK samples will be labelled in such a way that treatment allocation cannot be derived by the analytical site.

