## FLOW CHART - IV GROUP

Period	Visit	Day	Planned time (relative to first drug administration) [h:min]	Approximate clock time of actual day [h:min]	Event and comment	Safety laboratory	PK serum	12-lead ECG	Vital signs (BP, PR)	Questioning for AEs and concomitant therapy 	Query regarding local tolerability 
SCR	1	-21 to -3			Screening (SCR) 	x		x	x		
	2	-2	-48:00	8:00	Ambulatory visit	x 				x	
		-1	-14:00	18:00	Admission to trial site	x 				x	
		1	-3:00	06:00	Allocation to treatment 	x 	x 	x 	x 	x 	
			0:00	08:00	Drug administration start of infusion						
			0:30	08:30	end of infusion		x	x		x	x
			2:00	10:00	Light breakfast 		x	x	x		x
			4:00	12:00			x	x	x	x	
			8:00	16:00	Snack (voluntary) 		x	x	x		
			12:00	20:00			x	x	x	x	x
			24:00	08:00	Breakfast 	x	x	x	x	x	
			34:00	18:00	Dinner 		x		x	x	
			48:00	08:00	Breakfast  , discharge from trial site (confirmation of fitness) 		x	x	x	x	
		4	72:00	08:00	Ambulatory visit		x				x
		6	120:00	08:00	Ambulatory visit		x				x
		8	168:00	08:00	Ambulatory visit	x	x	x	x	x	
		11	240:00	08:00	Ambulatory visit		x				x
		14	312:00	08:00	Ambulatory visit	x	x	x	x	x	
		21	480:00	08:00	Ambulatory visit		x	x	x	x	
		28	648:00	08:00	Ambulatory visit	x	x	x	x	x	
		56	1320:00	08:00	Ambulatory visit	x	x	x	x	x	
FU	3	56 to 59			End of trial (EoTrial) examination 	x		x	x	x	x

1. Subject must be informed and written informed consent obtained prior to starting any screening procedures. Screening procedures include physical examination, check of vital signs, inclusive body temperature if it is still needed based on the status of pandemic, ECG, safety laboratory (including drug screening), demographics (including determination of body height and weight, smoking status and alcohol history), relevant medical history, concomitant therapy and review of inclusion/exclusion criteria.
2. The time is approximate; the procedure is to be performed and completed within the 3 h prior to drug administration.
3. If several actions are indicated at the same time, the intake of meals will be the last action.
4. At the end of trial visit the EoTrial examination includes physical examination, vital signs, ECG, safety laboratory, recording of AEs and concomitant therapies. EOT to be performed not before last PK sampling.

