## FLOW CHART - SC GROUP

Period	Visit	Day	Planned time (relative to first drug administration) [h:min]	Approximate clock time of actual day [h:min]	Event and comment	Safety laboratory	PK serum	12-lead ECG	Vital signs (BP, PR)	Questioning for AEs and concomitant therapy 	Query regarding local tolerability 
SCR	1	-21 to -3			Screening (SCR) 	x		x	x		
	2	-2	-48:00	8:00	Ambulatory visit	x 			x	x	
		-1	-14:00	18:00	Admission to trial site	x 				x	
		1	-3:00	06:00	Allocation to treatment 	x 	x 	x 	x 	x 	
			0:00	08:00	Drug administration/injection						x
			0:30	08:30						x	x
			1:00	09:00					x	x	
			1:30	09:30					x	x	
			2:00	10:00	Light breakfast 			x	x	x	
			3:00	11:00				x	x	x	
			4:00	12:00			x	x	x	x	x
			8:00	16:00	Snack (voluntary) 			x	x	x	
			12:00	20:00			x	x	x	x	x
		2	24:00	08:00	Breakfast 	x	x	x	x	x	x
			3	48:00	08:00		x	x	x	x	x
		4	72:00	08:00	Breakfast  , discharge from trial site (confirmation of fitness  )	x		x	x	x	x
			5	96:00	08:00	Ambulatory visit		x		x	x
			6	120:00	08:00	Ambulatory visit		x		x	x
			7	144:00	08:00	Ambulatory visit	x	x	x	x	x
			8	168:00	08:00	Ambulatory visit		x		x	
			11	240:00	08:00	Ambulatory visit		x		x	
			14	312:00	08:00	Ambulatory visit	x	x	x	x	
			21	480:00	08:00	Ambulatory visit		x	x	x	
			28	648:00	08:00	Ambulatory visit	x	x	x	x	
			56	1320:00	08:00	Ambulatory visit	x	x	x	x	
FU	3	56 to 59			End of trial (EoTrial) examination 	x		x	x	x	

1. Subject must be informed and written informed consent obtained prior to starting any screening procedures. Screening procedures include physical examination, check of vital signs, inclusive body temperature if it is still needed based on the status of pandemic, ECG, safety laboratory (including drug screening), demographics (including determination of body height and weight, smoking status and alcohol history), relevant medical history, concomitant therapy and review of inclusion/exclusion criteria.
2. The time is approximate; the procedure is to be performed and completed within the 3 h prior to drug administration.
3. If several actions are indicated at the same time, the intake of meals will be the last action.

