#### **3.2 DISCUSSION OF TRIAL DESIGN, INCLUDING THE CHOICE OF CONTROL GROUP**

This study will explore the absolute bioavailability, safety, tolerability and pharmacodynamics following intravenous (IV) infusion or subcutaneous (SC) injection of BI 765080 in matched pairs of healthy male subjects (matching is done based on age and body weight, see Section [3.3](#)). By dosing test and reference treatment to a matched pair on the same day the influence of confounding factors can be reduced to a minimum.

The trial will be conducted open-label. Blinding is not possible because the treatments are distinguishable. The open-label treatment is not expected to bias results, since the study endpoints are derived from measurement of plasma concentrations of the analyte, which are provided by a bioanalytical laboratory that is blinded to treatment allocation.

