### **5.3 DRUG CONCENTRATION MEASUREMENTS AND PHARMACOKINETICS**

#### **5.3.1 Assessment of pharmacokinetics**

For the assessment of pharmacokinetics, blood samples will be collected at the time points indicated in the [Flow Chart](#). Date and clock times of drug administration and pharmacokinetic sampling will be recorded in the CRFs. The actual sampling times will be recorded and used for determination of pharmacokinetic parameters.

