### **5.3.2 Methods of sample collection**

#### **5.3.2.1 Blood sampling for pharmacokinetic analysis**

[figure not shown]
For quantification of BI 765080 concentrations in serum, 3mL of blood will be drawn from an antecubital or forearm vein into a serum collection tube (SST II Advance tube or equivalent) at the times indicated in the [Flow Chart](#). Blood will be withdrawn by means of either an indwelling venous catheter or by venepuncture with a metal needle.

The sample tubes will be inverted six times without shaking and left upright for at least 30 minutes to allow the sample to thoroughly clot. Serum is prepared by centrifugation for approximately 10 -15 minutes at approximately 1500 g to 2000 g at room temperature. Immediately transfer at least 0.5 mL serum from the collection tube into each of the labelled cryotubes.

[figure not shown]
At a minimum, the sample tube labels should list BI trial number, subject number, visit, and planned sampling time, aliquot #1 or #2, serum, and PK.

[figure not shown]
The time each aliquot was placed in the freezer will be documented. Until transfer on dry ice to the analytical laboratory, the aliquots will be stored upright at approximately -70°C/-94°F or below at the trial site. The second aliquot will be transferred to the analytical laboratory after the bioanalyst has acknowledged safe arrival of the first aliquot. At the analytical laboratory, the serum samples will be stored at approximately -70°C/-94°F or below until analysis.

After completion of the trial, the serum samples may be used for further methodological investigations (e.g. for stability testing). However, only data related to the analyte will be generated by these additional investigations. The study samples will be discarded after completion of the additional investigations but not later than 5 years after the CTR is archived.

Proprietary confidential information © 2021 Boehringer Ingelheim International GmbH or one or more of its affiliated companies

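### Do the PK tube labels let the bioanalytical laboratory work out each subject's arm, contrary to protocol section 4.1.5?

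*Protocol*

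**What the plan says.** The trial is open-label, and section 3.2 gives the reason: "Blinding is not possible because the treatments are distinguishable". It goes on to say that this should not bias results, because the endpoints come from measured concentrations "which are provided by a bioanalytical laboratory that is blinded to treatment allocation". Section 4.1.5 confirms that the trial is handled openly throughout, including data cleaning and preparation of the analysis. It makes one exception: "PK samples will be labelled in such a way that treatment allocation cannot be derived by the analytical site".

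The label itself is specified in section 5.3.2.1: "At a minimum, the sample tube labels should list BI trial number, subject number, visit, and planned sampling time", followed by aliquot number, matrix and the PK designation. Two aliquots of each sample reach the laboratory in turn: "The second aliquot will be transferred to the analytical laboratory after the bioanalyst has acknowledged safe arrival of the first aliquot".

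On timing, section 5.3.1 says that "blood samples will be collected at the time points indicated in the" Flow Chart. There are two of these, headed "FLOW CHART - IV GROUP" and "FLOW CHART - SC GROUP", with different sampling times.

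**The concern.** Section 4.1.5 promises that allocation cannot be derived, which is stronger than saying it is not stated. A planned time that exists in one arm only works as a treatment code for anyone who knows the schedules. The subject number then carries that information to every other tube from the same man. Because the label shows the planned time and not the actual one, timing deviations do not hide it.

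Section 3.2 uses laboratory blinding as part of its case for low bias. If the blinding is not real, a stated safeguard for the primary endpoints is missing. In principle, an analyst aware of the arm could treat repeat assays or doubtful results differently by arm, and so shift the SC/IV ratios of AUC and Cmax.

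**Working it through.** The plan gives no figure here to reproduce. The check compares the label rule with the two schedules, then asks what the laboratory could do with the information.

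**1. Label content.** The list in section 5.3.2.1 has no treatment, route or arm. It does have subject number and planned time.

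**2. PK times in each chart.**
- IV: pre-dose, 0:30, 2:00, 4:00, 8:00, 12:00, 24:00, 34:00, 48:00, 72:00, 120:00, 168:00, 240:00, 312:00, 480:00, 648:00 and 1320:00, which is 17.
- SC: pre-dose, 4:00, 12:00, 24:00, 48:00, 96:00, 120:00, 144:00, 168:00, 240:00, 312:00, 480:00, 648:00 and 1320:00, which is 14.

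Some SC rows have displaced columns in the text available. The 96:00 and 144:00 PK marks are therefore read after realignment, and the status of 0:30, 2:00, 8:00 and 72:00 in the SC arm is tested below. The 34:00 IV row needs no such repair.

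**3. Times found in one arm only.** With 14 subjects per arm, arm-specific tubes = 14 × (IV-only times) + 14 × (SC-only times), and all tubes = 14 × 17 + 14 × (SC times).

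| Reading of the SC chart | IV-only | SC-only | Arm-specific tubes | All tubes | Share |
|---|---|---|---|---|---|
| As listed | 0:30, 2:00, 8:00, 34:00, 72:00 | 96:00, 144:00 | 14×5 + 14×2 = 98 | 14×17 + 14×14 = 434 | 22.6% |
| 72:00 also SC | 0:30, 2:00, 8:00, 34:00 | 96:00, 144:00 | 14×4 + 14×2 = 84 | 14×17 + 14×15 = 448 | 18.8% |
| 0:30, 2:00, 8:00 and 72:00 also SC | 34:00 | 96:00, 144:00 | 14×1 + 14×2 = 42 | 14×17 + 14×18 = 490 | 8.6% |

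The share depends on how a damaged table is read and is not the useful number. In every reading, each IV subject has at least one arm-specific time and each SC subject has two. With complete sampling, 14 + 14 = 28 of 28 subjects can be classified.

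**4. Conditions for the inference.** A tube at a shared time, such as 24:00, reveals nothing alone. The reader needs the full set of labels for a subject and both charts. Without the charts, the labels sort subjects into two groups but do not say which is SC. The documents do not say whether the laboratory has the charts. An SC subject who left before 96:00 would have no SC-only label.

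**5. Where knowledge of the arm could act.**
- PK parameters are calculated from concentrations and actual sampling times (protocol 5.3.1) in standard software (SAP section 3).
- Exclusions for protocol violations are decided by the Report Planning Meeting at the latest, and non-evaluability is identified during data analysis (protocol 7.3, SAP 6.2). Under section 4.1.5 these steps are open by design, whatever the label says.
- The secondary safety endpoint, drug-related adverse events, is judged by an unblinded investigator. Laboratory blinding never protected it.
- No laboratory decision that depends on the arm is described.

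**6. What a change would buy.**
- Rewording 3.2 and 4.1.5 changes no sample, assay, parameter or interval.
- Coded labels would remove subject number, visit and planned time, and would require a key linking each tube, in two aliquots, back to subject and time. A linkage error would put a concentration in the wrong profile, and so into AUC or Cmax, in a trial with 14 subjects per arm.

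**The case for a change.** The best case for acting is that the protocol makes an absolute statement which its own label rule does not support, and section 3.2 relies on it. The correction costs one sentence. SAP section 4 already corrects another protocol wording error, plasma for serum, so there was a natural place for it. Left alone, the claim could be repeated in the clinical trial report. A promise that holds only while the laboratory does not know the schedules is not a property of the labels.

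The textual part stands. The sentence in 4.1.5 is too strong, and 34:00 alone is enough to show it. What does not follow is a consequence for the trial. Section 3.2 justifies the open label by the treatments being distinguishable and argues low bias first from endpoints that are measured concentrations. The blinded laboratory is an added support. Section 4.1.5 separately accepts open handling on the ground that the potential for bias is low. A corrected sentence would largely restate reasoning already there.

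**Conclusion.** The inconsistency is real but is an overstatement in a supporting sentence, and no change to the protocol or SAP is needed. If sampling is complete and the reader has both flow charts, the arm of all 28 subjects can be inferred. If the laboratory lacks the charts, the labels show only that two schedules exist. In neither case do the documents show a route from that knowledge to a different AUC or Cmax, and no bias has been demonstrated.

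Keeping subject number and planned time on the tube is a fair trade-off. It gives direct traceability for concentrations that feed the primary endpoints, at the price of a laboratory mask that can be seen through.

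The conclusion rests on three assumptions: concentrations are reported as assayed, without arm-dependent handling; the 96:00 and 144:00 SC marks are PK samples once the displaced columns are realigned; and the flow charts are followed. If the second fails, 34:00 still separates the arms, less directly: its presence marks an IV subject, and its absence in an otherwise complete set marks an SC subject.

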#### **4.1.6 Packaging, labelling, and re-supply**

The investigational medicinal products will be provided by BI. They will be packaged and labelled in accordance with local law and the principles of Good Manufacturing Practice.

For details of packing and the description of the label, refer to the ISF.

The name, address and telephone number of the trial site are provided in the subject information form. The EudraCT number is indicated on the title page of this protocol as well as on the subject information and informed consent forms.

No re-supply is planned.

#### **4.1.7 Storage conditions**

Drug supplies will be kept in their original packaging and in a secure limited access storage area in accordance with the recommended (labelled) storage conditions. If necessary, a temperature log must be maintained to make certain that the drug supplies are stored at the correct temperature. If the storage conditions are found to be outside the specified range, the local clinical monitor (as provided in the list of contacts) is to be contacted immediately.

#### **4.1.8 Drug accountability**

The investigator or designee will receive the investigational drugs delivered from the sponsor following requirements are fulfilled:

- Approval of the clinical trial protocol by the IRB / ethics committee
- Availability of a signed and dated clinical trial contract between the sponsor and the investigational site
- Approval/notification of the regulatory authority, e.g. competent authority
- Availability of the *curriculum vitae* of the Principal Investigator
- Availability of a signed and dated clinical trial protocol

Only authorised personnel documented in the form 'Trial Staff List' may dispense medication to trial subjects. The trial medication must be administered in the manner specified in the CTP.

The investigator or designee must maintain records of the product's delivery to the trial site, the inventory at the site, the use by each subject, and the disposal of unused products. These records will include dates, quantities, batch / serial numbers, expiry ('use-by') dates, and the unique code numbers assigned to the investigational medicinal product and trial subjects. The investigator or designee will maintain records that document adequately that the subjects were provided the doses specified by the CTP and reconcile all investigational medicinal products received from the sponsor. At the time of disposal of remaining trial medication, the investigator or designee must verify that no remaining supplies are in the investigator's possession.

All unused medication will be disposed of locally by the trial site upon written authorisation of the trial clinical monitor. Receipt, usage and disposal of trial medication must be documented on the appropriate forms. Account must be given for any discrepancies.

#### **4.2 OTHER TREATMENTS, EMERGENCY PROCEDURES, RESTRICTIONS**

##### **4.2.1 Other treatments and emergency procedures**

There are no special emergency procedures to be followed. No additional treatment is planned. However, if adverse events require treatment, the investigator can authorise symptomatic therapy. In those cases, subjects will be treated as necessary and, if required, kept under supervision at the trial site or transferred to a hospital until all results of medical evaluations are acceptable.

##### **4.2.2 Restrictions**

###### **4.2.2.1 Restrictions regarding concomitant treatment**

In principle, no concomitant therapy is allowed. All concomitant or rescue therapies will be recorded (including time of intake on study days) on the appropriate pages of the CRF.

Proprietary confidential information © 2021 Boehringer Ingelheim International GmbH or one or more of its affiliated companies

